
Background and Rationale:
	
Severe acute respiratory syndrome coronavirus 2 (SARS-CoV-2) has spread globally since December 2019 causing a pandemic of Coronavirus disease 19 (COVID-19) in almost all countries worldwide. The clinical spectrum of COVID-19 ranges from asymptomatic carriers to respiratory failure requiring respiratory support in the intensive care unit (ICU). Systemic hyperinflammation is a hallmark of more severe stages of COVID-19 leading to acute respiratory distress syndrome, mechanical ventilation and ultimately death. In this stage, COVID-19 is associated with a decrease in suppressor and regulatory T cell counts and an extensive release of proinflammatory cytokines and biomarkers called a cytokine storm, which is thought to be the major driver of severe pneumonia caused by SARS-CoV-2.
 
No proven or approved effective treatment for COVID-19 infection currently exists. The mechanism responsible for virus-induced hyper-activation of the host immune system remains poorly understood but likely involves several immune cells and inflammatory plasmatic cascades such as the complement and the kinin-kallikrein (KK) system. The complement system (CS) is an integral part of the innate immune system and consists of a number of distinct plasma proteins that act as a first line of defence inducing an inflammatory response after opsonisation of pathogens and dying cells. Previous evidence indicated that an over-activated complement systems, driven by the lectin pathway of complement in particular, seems to contribute to ALI in response to infection with CoV such as SARS-CoV-2 leading to the clinical picture of severe COVID-19 pneumonia and consequently to ARDS.
 
The KK system is a plasmatic cascade that after activation (shear stress of vessels, e.g. during vascular inflammation) and subsequent cleavage of kininogen by kallikrein releases bradykinin. Bradykinin binds to B2-receptors on endothelial cells leading to capillary leakage and angioedema. After enzymatic degradation bradykinin products may also bind to B1-receptors on endothelial cells that are upregulated under proinflammatory conditions and have strong vasopermeable capacity. Although direct evidence is lacking, several facts argue for an involvement of bradykinin in pulmonary angioedema observed in COVID-19, in particular a reduced activity of ACE2 caused by SARS-CoV-2 leading to a relative abundance of bradykinin degradation production with subsequent B1 activation and local pulmonary edema.
 
C1 esterase inhibitor (C1INH) is a member of the serpin superfamily of serine-protease inhibitors and is a strong inhibitor of the CS and KK system among others. Conestat alfa is a recombinant human C1INH, that shares an identical protein structure with plasma-derived C1INH. Although data on C1INH treatment in the context of SARS-CoV-2 infection are lacking, results from previous studies suggest that C1INH treatment may reduce the collateral damage caused by hyperinflammation in human sepsis. The rationale of the current trial is based upon the following assumptions: In the context of COVID-19, conestat alfa treatment may 1) dampen uncontrolled complement activation and collateral lung damage and 2) reduce capillary leakage and subsequent pulmonary edema by direct inhibition of KK system.
 
Hypothesis: Administration of conestat alfa for 72 hours in addition to standard of care (SOC) in patients hospitalized with non-critical SARS-CoV-2 pneumonia (WHO Ordinal Scale Score 3 or 4) will be associated with a reduced clinical severity on day 7 after inclusion and a lower risk of disease progression to ALI and ARDS.

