Inclusion / Exclusion criteria:	
Patients admitted for the management of confirmed COVID-19 will be approached.
 
Inclusion criteria: Male or female of age 18-85 years, admitted to the hospital because of confirmed (by a positive SARS-CoV-2 PCR result) COVID-19 infection, evidence of pulmonary involvement on CT scan or X-ray of the chest, symptom onset within the previous 10 days AND at least one additional risk factor for progression to mechanical ventilation: 1) arterial hypertension, 2) ≥50 years, 3) obesity (BMI≥30.0 kg/m²), 4) history of cardiovascular disease, 5) chronic pulmonary disease, 6) chronic renal disease, 7) C-reactive protein of >35mg/L, 8) oxygen saturation at rest in ambient air of ≤94%.
 
Exclusion criteria: Contraindications to the class of drugs under study (C1 esterase inhibitor), treatment with tocilizumab or another IL-6R or IL-6 inhibitor before enrolment, History or suspicion of allergy to rabbits, pregnancy or breast feeding, active or planned treatment with any other complement inhibitor, liver cirrhosis (any Child-Pugh score), currently admitted to an ICU or expected admission within the next 24 hours, currently receiving invasive or non-invasive ventilation (with the exception of high-flow oxygen therapy), participation in another study with investigational drug within the 30 days preceding (with the exception of other COVID-19 studies)

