5.3 Other Outcomes of Interest

- Changes in the ordinal WHO scale from baseline over 14 days
- Length of hospital stay until day 28 in survivors.
- Proportion of participants progressing to mechanical ventilation on day 7 and day 14
- Proportion of participants requiring ICU treatment on day 7 and 14
- Length of ICU stay until day 28
- Ventilator-free days until day 28
- All-cause mortality (time from randomisation to death within four weeks)
- Changes in biomarker levels until day 14: CRP, LDH, D-dimer, ferritin, IL-6, lymphocyte count
- Time to virological clearance of SARS-CoV-2 by PCR from upper or lower respiratory tract samples (time from enrolment to first of 2 negative assays at least 12 hours apart)
- Proportion of patients receiving additional anti-inflammatory treatment such as tocilizumab or immunoglobulins within 14 days
- Time to defervescence (temperature <38.0°C sustained for at least 48 hours)
- Time to clinical improvement (defervescence, normalization of oxygen saturation (>93%) and respiratory rate) until day 28
- Duration of supplemental oxygen until day 28
- Incidence of acute kidney injury classified on the basis of the worst serum creatinine according to the KDIGO classification, and changes of serum creatinine and estimated glomerular filtration rate (eGFR, estimated with the CKD-EPI equation) from baseline
- In a subgroup of patients (in Basel and optional in other centers) the pharmacokinetics and pharmacodynamics of conestat alfa in COVID-19 patients will be characterized by measuring the concentration of conestat alfa and the activity of C1INH, inflammatory cytokines and proteins (such as C4d, C5a, sC5-b9, IL-10) and parameters of the contact activation and coagulation cascade (such as factor XII and pre-kallikrein). In addition, changes of urinary markers of renal injury (such as NGAL, KIM-1, osteopontin and clusterin) from baseline will be analysed.

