- Currently admitted to an ICU or expected admission within the next 24 hours
- Currently receiving invasive or non-invasive ventilation (with the exception of high-flow oxygen therapy).
- In the opinion of the treating time, death is deemed to be imminent and inevitable within the next 24 hours
- Participation in another study with investigational drug within the 30 days preceding and during the present study with the following exemptions: 1) participation in COVID-19 drug trials started at least 48 hours before admission (e.g. postexposure prophylaxis with hydroxychloroquine) and 2) participation in COVID-19 drug trials during ICU admission
- Previous enrolment into the current study
- Enrolment of the investigator, his/her family members, employees and other dependent persons

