9.2.3 Assessment of other outcomes of interest

- The following assessments will be performed during the study: changes in WHO ordinal scale, ICU admission/discharge date, mechanical ventilation start/end date, admission/discharge date, all-cause mortality at 4 weeks
- The receipt of additional anti-inflammatory treatments such as tocilizumab will be recorded within 14 days
- Vital signs will be recorded during 14 days until discharge to determine the time to defervescence and clinical improvement
- For the analysis of virological clearance of SARS-CoV-2, samples from the upper or lower respiratory tract will be collected at baseline (if not already performed on admission) to confirm SARS-CoV-2 infection and again on day 4-7 and day 14/discharge (only when discharged on day 10-13). Subsequently, samples will be analysed at the central laboratory of the study site using a quantitative assay according to validated standard in-house procedures. A negative result will be confirmed by a second test at least 12 hours apart.
- For the analysis in changes of biomarker levels CRP- LDH, D-dimer, IL-6 and lymphocytes will be measured in blood samples collected on day 0, 1-3 and every second day afterwards until day 14 or discharge. Blood samples will be sent to and analysed by validated methods in the central laboratory of respective study sites according to standard in-house procedures
- The incidence of acute kidney injury will be evaluated according to the KDIGO classification. Baseline creatinine will be defined as a concentration obtained within a 12-month period before admission and considered to be representative of the baseline kidney function according to the judgment of the treating physician. If this reference value is not available, the minimum of either serum creatinine at the time of admission or study inclusion, or in patients without chronic kidney disease, a calculated serum creatinine concentration using the MDRD equation will be used.

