9.2.4.3 Vital signs

No study specific vital signs will be assessed. All patients will be monitored regarding blood pressure, heart rate, respiratory rate and oxygen saturation as per standard operating procedures for the treatment of COVID-19 patients.

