9.3 Procedures at each visit

9.3.1 Split into subtitles by type of visit

Visit 1, Screening (Day -1 or day 0):

Informed consent will be obtained before any study-specific tests or evaluations will be performed.

- Patients who are admitted to the medical ward with confirmed or suspected SARS-CoV-2 infection will be screened within 72 hours after admission on the ward. Screening will be based on routinely available data and laboratory tests with only the pregnancy test as study-specific intervention/test if necessary before screening of the patients. Results from prior tests that will be used for screening potentially eligible subjects will be recorded in the eCRF.
- Selection of potential participants according to inclusion and exclusion criteria.
- Explanation of patient information including study purpose and signature of informed consent form.
- Study enrolment
- Assignment of the trial subject identification number
- Pregnancy test if applicable.
- Eligibility check (in- and exclusion criteria)
- Randomisation, which can either occur on the same day of hospital admission or within 72 hours after hospital admission.

Visit 2, Intervention period (Day 0)

- Assessment of demographics, medical history and concomitant medication
- Assessment of vital signs including respiratory rate.
- Assessment of WHO ordinal scale and need for oxygen supplementation
- Collection of blood (12ml) for analysis of ferritin, IL-6, D-Dimer, C1INH concentration, and in Basel (optional for other centers): collection of blood (5ml) and urine (5ml) for the analysis of complement proteins, parameters of the contact activation and coagulation system, renal injury markers, and inflammatory cytokines. Routine full blood count, coagulation and biochemistry studies will only be performed if results from prior tests on the same day are not available.
- Assessment of reference serum creatinine
- Virology testing (quantitative SARS-CoV-2 PCR) on a nasopharyngeal sample if not already performed before inclusion into the study. This is optional for other centers except Basel.
- Following randomisation, participants in the active treatment group will receive 8400 U of conestat alfa as slow intravenous injection. The time of dosing and the dose will be recorded. Subsequently, 4200 U will be administered every 8 hours in the active trial group.
- AEs occurring after the administration will be recorded.

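### The exploratory time-to-clinical-improvement outcome sets no ambient-air condition on saturation, and its day-28 horizon outruns the vital-sign recording it depends on

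*Protocol*

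**What the plan says.** Section 5.3 defines the outcome as "Time to clinical improvement (defervescence, normalization of oxygen saturation (>93%) and respiratory rate) until day 28". The bullet before it defines defervescence as a temperature below 38.0°C held for at least 48 hours. A separate bullet in the same list is "Duration of supplemental oxygen until day 28"; it is not linked to the improvement outcome.

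Section 9.2.3 says how the data arise: "Vital signs will be recorded during 14 days until discharge to determine the time to defervescence and clinical improvement". Section 9.2.4.3 adds "All patients will be monitored regarding blood pressure, heart rate, respiratory rate and oxygen saturation as per standard operating procedures". A footnote to the schedule in section 9.1 states that the worst vital-sign value of each day is the one documented.

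For eligibility, by contrast, the saturation risk factor (94% or lower) is worded "oxygen saturation at rest in ambient air of" that level, in both the synopsis and section 7.1.

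**The concern.** Measured saturation depends on how much oxygen the patient is receiving. Without a breathing condition, a value above 93% may mean that the lungs have recovered or that oxygen is holding the value up. Oxygen is part of standard care in both arms, and patients already on it are in the target population. An outcome called clinical improvement could then be reached by patients who still need respiratory support.

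The horizon is a second, independent matter. An outcome cannot run to day 28 on measurements whose scheduled recording ends around day 14.

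**Working it through.** There is no stated figure to reproduce, so the check sets the relevant sections side by side.

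**1. Is ambient air required anywhere for this outcome?**

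| Place in the protocol | What it gives on saturation | Ambient air or off oxygen? |
|---|---|---|
| 5.3, outcome definition | >93% | Not stated |
| 9.2.3, assessment | Vital signs recorded | Not stated |
| 9.2.4.3, vital signs | Monitored under routine procedures | Not stated |
| 9.1, schedule footnote | Worst value of the day | Not stated |
| Synopsis and 7.1, eligibility | 94% or lower as a risk factor | Ambient air, at rest |

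The qualifier appears only at entry.

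**2. Can supported patients be in the trial, and from when?** The synopsis hypothesis names patients at "WHO Ordinal Scale Score 3 or 4", and score 4 is oxygen by mask or nasal prongs. Section 7.1 excludes patients "Currently receiving invasive or non-invasive ventilation (with the exception of high-flow oxygen therapy"), so high-flow patients (score 5) are not excluded by that criterion. Patients who deteriorate can reach score 5 or 6 later. A patient at score 4 or 5 on day 0 whose worst saturation that day is 95% meets the saturation component on day 0.

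**3. What limits the effect?** Saturation is one of three components, and the other two must also be met. Because the worst daily value is used, one reading of 93% or lower fails that day. A supported patient whose saturation stays above 93% all day still passes.

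**4. Comparison with the secondary endpoint of the same name (section 5.2).** That endpoint needs a two-point gain on the WHO scale or live discharge. A patient who enters at score 4 and stays in hospital at score 4 has gained 4 − 4 = 0 points and has not improved. Under section 5.3 the same patient can count as improved once fever and respiratory rate are also met.

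**5. Horizon.** The outcome runs to day 28. Section 9.2.3 records vital signs for 14 days or until discharge. The schedule in section 9.1 has them up to the visit at day 14 (+/-2 days) or discharge and none at week 4. The week-4 contact in section 9.3.1 lists adverse events, WHO scale, ICU admission and ventilation, but no vital signs. The uncovered span is 28 − 14 = 14 days (28 − 16 = 12 at the edge of the visit window), and longer for anyone discharged before day 14.

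**6. Do the data for a repair exist?** Yes. Visits 2 to 6 include "Assessment of WHO ordinal scale and need for oxygen supplementation", and section 9.2.2 has the worst WHO status recorded daily to day 14. Score 3 means in hospital without oxygen. On a day whose worst score is 3, every saturation reading was therefore taken in ambient air.

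**The case against.** The strongest reply is that this is one bullet in a long list of outcomes that section 11.4.3 assigns to descriptive and exploratory analysis. No alpha, sample size or stopping rule rests on it. Oxygen dependence is captured by the oxygen-duration outcome, the daily WHO scale and the secondary endpoint. The bullet gives no respiratory-rate cut-off either, so it may be shorthand to be completed in the SAP.

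The low stakes stand. The SAP argument stands only in part. For these outcomes the synopsis names the statistical tests as what will follow in the SAP; the saturation rule itself is given in the protocol. Applied as given, it lets oxygen support satisfy the component.

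Some stronger readings are tempting but not supported:

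- **That supported patients do count as improved.** The text does not say so; it fails to prevent it. The other components and the worst-value rule still apply.
- **That the saturation component is inert for most of the trial.** The protocol gives neither the share of patients on oxygen at entry nor how often supported patients stay above 93% all day.
- **That the entry and outcome cut-offs conflict.** A saturation of 94% in ambient air is a risk factor at entry and already above the outcome threshold. But the entry criterion is one of eight alternative risk factors for progression, not a definition of abnormal, and the two thresholds need not be complements.
- **That nothing can be known after day 14.** Patients still admitted have a study visit at week 4, and charts may be reviewed. It is the scheduled recording that stops.

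**Conclusion.** The point holds as an omission and an internal contradiction in one exploratory outcome. The saturation component can be met through oxygen support, possibly from day 0. The day-28 horizon contradicts recording that ends at about day 14 or at discharge.

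The effect of the omission cannot be sized from the protocol. It ranges from no supported patients (if each dips to 93% or lower on every supported day) to all of them (if none does), and in either case fever and respiratory rate must also be met. The horizon gap is up to 14 of 28 days, or more after early discharge. The trial is open-label, so a reader might infer that oxygen titration by unblinded staff biases the comparison of arms. Nothing in the protocol shows the direction or size of such an effect. The primary and secondary results are unaffected.

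This rests on reading the definition as written. An SAP that is not shown could add the condition.

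**What to change.** Amend the outcome in section 5.3 and align section 9.2.3:

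- Keep the >93% cut-off but require it in ambient air. Count any day on supplemental oxygen, high-flow oxygen or ventilation as not normalised, using the oxygen need and WHO score already recorded. This is a classification rule; it needs no new measurement, no trial off oxygen and no change to care.
- End the horizon at day 14, where the scheduled vital signs end. State how patients discharged earlier without an event are handled, since their recording stops at discharge.
- Report per arm how many patients meet all components at baseline, and keep them in the analysis so that the comparison stays with all randomised patients.

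The cost is a few lines of wording. The downside is fewer and later events and a shorter horizon.

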5.4 Safety Outcomes

The study will evaluate the safety of conestat alfa in the setting of COVID-19 infections if added to SOC compared to SOC treatment only by measuring the incidence of adverse events up to 4 weeks inclusion.

6. STUDY DESIGN

6.1 General study design and justification of design

This is an investigator-initiated, exploratory, randomized, parallel-group, open-label, multi-center, phase 2 clinical study in patients with confirmed COVID-19 infection and admitted to the hospital for treatment of SARS-CoV-2 infection to estimate the effect size of conestat alfa treatment in addition to standard of care compared to only standard of care on the proportion of patients surviving without requiring mechanical ventilation.

The study will recruit approximately 120 patients (80 patients in the intervention and 40 in the control arm) from several sites in Switzerland, Brazil and Mexico. Sites will be selected on the basis of estimated numbers of cases, the availability of a committed principal site investigator and research team, and the capacity to collect samples as per protocol.

Participants will be randomly assigned in a 2:1 ratio to conestat alfa treatment in addition to standard of care or only standard of care stratified by the site. Screening, informed consent and randomisation will happen as early as possible after admission to the hospital, usually within 72 hours after admission. Participants will receive intravenous conestat alfa or no additional treatment during a 72-hour period usually starting on the day of informed consent (=day 0). Both groups will continue to receive SOC treatment for COVID-19 infection. Blood samples will be collected before and during the 72-hour administration period. Follow-up will include the period until discharge and a telephone interview at four weeks (+/- one week) if participants are discharged earlier to assess potential adverse events.

Duration of participant's participation will be 4 weeks (+/- 5 days). Screening phase duration is up to 72 hours; treatment phase is a maximum of 72 hours, and follow-up period is 4 weeks after enrolment. At least three attempts will be made to contact the participant or his person of confidence at week 4 before the participant may be considered as lost to follow-up.

6.2 Methods of minimising bias

Unmeasured confounding and bias will be minimised by randomisation and objective endpoints.

6.2.1 Randomisation

Participants will be randomized to two parallel groups in a 2:1 ratio in an open-label controlled design to receive either conestat alfa (intervention) in addition to standard of care (SOC) or SOC only (control). Randomisation will be stratified by the study site before inclusion using permuted-block randomization with varying block sizes. Allocation will be concealed, and randomization implemented via the electronic data capture system software SecuTrial®.

6.2.2 Blinding procedures

Participants, treating physicians, nurses, investigators and DSMB members will not be blinded.

6.2.3 Other methods of minimising bias

Not applicable.

6.3 Unblinding Procedures (Code break)

Not applicable.

7. STUDY POPULATION

Patients admitted for the management of confirmed COVID-19 infection will be approached. If enrolment goals are not met expansion to other centers in Switzerland, Brazil and Mexico will be explored.

7.1 Eligibility criteria

Participants fulfilling all of the following inclusion criteria are eligible for the study:

- Informed Consent as documented by signature
- Age 18-85 years
- Females or Males
- admitted to the hospital because of confirmed (by a positive SARS-CoV-2 PCR result) COVID-19 infection
- evidence of pulmonary involvement on CT scan or X-ray of the chest (e.g. ground glass opacities)
- symptom onset within the previous 10 days, i.e. fever or one respiratory symptom (patients presenting later may have already progressed to an inflammatory state that is potentially not amenable to C1INH treatment). Respiratory symptoms include cough, sore throat, hemoptysis, shortness of breath, runny nose, or chest pain.
- expected to remain an inpatient over the next three calendar days from time of enrolment
- at least one additional risk factor for progression to mechanical ventilation: 1) arterial hypertension, 2) ≥ 50 years, 3) obesity ($BMI \geq 30.0$ kg/m²), 4) cardiovascular disease, 5) chronic pulmonary disease, 7) chronic renal disease, 6) C-reactive protein of >35 mg/L, 7) oxygen saturation at rest in ambient air of $\leq 94\%$. Cardiovascular disease includes a history of coronary artery disease, cerebrovascular disease, peripheral artery disease, rheumatic heart disease, congenital heart disease and of recent (< 3 months) deep vein thrombosis or pulmonary embolism. Chronic pulmonary disease includes a history of chronic obstructive pulmonary disease, asthma, occupational lung disease, interstitial lung disease or of pulmonary hypertension. Chronic renal disease is defined as a history of an estimated glomerular filtration rate (according to the Chronic Kidney Disease Epidemiology Collaboration equation) < 60 ml/min/1.73 m² for at least three months.

The presence of any one of the following exclusion criteria will lead to exclusion of the participant, for example:

- Age >85 years
- Contraindications to the class of drugs under study (C1 esterase inhibitor), e.g. known hypersensitivity or allergy to class of drugs or the investigational product
- Treatment with tocilizumab or another IL-6R or IL-6 inhibitor before enrolment
- History or suspicion of allergy to rabbits
- Women who are pregnant or breast feeding
- Active or planned treatment with any other complement inhibitor
- Liver cirrhosis (any Child-Pugh score)
- Incapacity or inability to provide informed consent
- Currently admitted to an ICU or expected admission within the next 24 hours
- Currently receiving invasive or non-invasive ventilation (with the exception of high-flow oxygen therapy).
- In the opinion of the treating time, death is deemed to be imminent and inevitable within the next 24 hours
- Participation in another study with investigational drug within the 30 days preceding and during the present study with the following exemptions: 1) participation in COVID-19 drug trials started at least 48 hours before admission (e.g. postexposure prophylaxis with hydroxychloroquine) and 2) participation in COVID-19 drug trials during ICU admission
- Previous enrolment into the current study
- Enrolment of the investigator, his/her family members, employees and other dependent persons

